12.0 TOXICITIES/SIDE EFFECTS

12.1 Sorafenib

1. Cardiac ischemia and/or infarction: The incidence of cardiac ischemia/infarction was 2.7% in NexavarTM patients compared with 1.3% in the placebo group and in patients treated with renal cell carcinoma. Temporary or permanent discontinuation of NexavarTM should be considered in patients who develop cardiac ischemia and/or infarction.
2. Risk of hemorrhage: An increased risk of bleeding may occur following NexavarTM administration. In the SHARP trial, an excess of bleeding regardless of causality was not apparent and the rate of bleeding from esophageal varices was 2.4% in NexavarTM patients and 4% in placebo patients.
3. Hypertension: Blood pressure should be monitored weekly during the first 6 weeks of NexavarTM therapy and thereafter monitored and treated, if required, in accordance with standard medical practice. In the SHARP trial, hypertension was reported in approximately 9.4% of NexavarTM - treated patients and 4.3% of patients in the placebo group.
4. Dermatologic: Hand-foot skin reaction and rash represent the most common adverse reactions attributed to NexavarTM. Rash and hand-foot skin reaction are usually CTCAE Grade 1 and 2 and generally appear during the first six weeks of treatment with NexavarTM. Management of dermatologic toxicities may include topical therapies for symptomatic relief, temporary treatment interruption and/or dose modification of NexavarTM, or in severe or persistent cases, permanent discontinuation of NexavarTM.

12.2 Bavituximab

1. Thromboembolic events: in the initial studies administering bavituximab for patients with chronic HCV infection there were no reports of

thromboembolic events including arterial thrombosis or venous thrombosis (deep vein thrombosis or pulmonary embolism). In later studies combining bavituximab and chemotherapy in cancer patients there was a small increase in thromboembolic events. These events were mainly deep vein thrombosis or pulmonary embolism. There were no fatal events attributable to these adverse events and it is unclear whether the events were a direct result of combined chemotherapy or the inherent risk of thromboembolic events seen in cancer patients.

2. Infusion reactions: Bavituximab is a chimeric antibody and some patients may experience side effects associated with monoclonal antibody therapy, including allergic/hypersensitivity reactions or cytokine release syndrome/acute infusion reactions. There is significant overlap between these reactions, with common manifestations including (but not limited to): drug fever, flushing, rash, dyspnea, bronchospasm, or hypotension. In studies investigating bavituximab in combination with chemotherapy, pre-medication with antihistamines and/or steroids was administered resulting in 20-30% Grade I or II adverse infusion reactions. These have been generally well tolerated, and have not required an alteration in bavituximab dosing.
3. Prolonged coagulation times: Prolonged coagulation times (e.g., aPTT) have been observed in preclinical and clinical studies that are not associated with significant bleeding. In clinical studies, prolongation of aPTT has been noted at the highest doses administered (3 and 6 mg/kg). This concentration- dependent, transient and reversible phenomenon is believed to be due to *in vitro* assay interference and does not pose a significant bleeding risk to patients.
4. Gastrointestinal: Nausea, vomiting and anorexia occur infrequently and are self-limiting without additional treatment.

Because of the potential for thrombogenicity with agents such as bavituximab, patients will be monitored for the development of thromboembolic events as follows:

- Regular assessment of blood coagulation parameters (PT, INR, aPTT). Regular screening for potential arterial or venous thromboses during physical examination
- Regular bilateral lower extremity venous doppler ultrasound

Thrombotic/thromboembolic events including, but not limited to, superficial thrombophlebitis, deep vein thrombosis, pulmonary embolism, cerebrovascular accident, ischemic stroke, coronary thrombosis, myocardial infarction, myocardial ischemia (including isolated ECG findings), arterial embolism, arterial thrombosis, catheter-related thrombosis, or intra-abdominal thromboembolism should be captured as an adverse event. Tumor thrombus is not a thrombotic/thromboembolic event and will not be captured as an AE.

Note: Elevated d-dimer alone does not constitute a thrombotic AE and should not be captured as such.

13.0 CRITERIA FOR THERAPEUTIC RESPONSE/OUTCOME ASSESSMENT (Phase II Component)

For the purposes of this study, patients will be evaluated for response at 2 weeks after the first cycle of bavituximab and every 6 weeks thereafter. RECIST criteria are included below.

13.1 Definitions

Response and progression will be evaluated in this study using the new international criteria proposed by the Response Evaluation Criteria in Solid Tumors (RECIST) Committee [*JNCI* 92(3):205-216, 2000]. Changes in only the largest diameter (unidimensional measurement) of the tumor lesions are used in the RECIST criteria. Note: Lesions are either measurable or non-measurable using the criteria provided below. The term “evaluable” in reference to measurability will not be used because it does not provide additional meaning or accuracy.

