	
 2. Locally advanced or metastatic disease. 
 a. Patients with locally advanced disease must have disease deemed to be unresectable or not eligible for hepatic transplantation by surgical oncologist or transplant physician 3. Measurable disease, defined as lesions that can accurately be measured in at least one dimension (longest diameter to be measured) according to Response Evaluation Criteria in Solid Tumors (RECIST, version 1.1) at least 2 cm with conventional techniques or at least 1 cm with spiral computed tomography. 4. Child-Pugh Score A or B7. 5. Age \geq 18 years. 6. ECOG Performance Score of 0-2. 7. Absolute neutrophil count \geq 1,200 cells/mm³. 8. Platelet count \geq 70,000 cells/mm³. 9. Total Bilirubin \leq 3.0 mg/dl. 10. Hemoglobin \geq 8.5 g/dl. 11. INR \leq 1.8 (therapeutic anticoagulation allowed as long as medically indicated.) 12. Creatinine \leq 1.5 times upper limit of normal. 13. Women of childbearing potential must have a negative pregnancy test. 14. No clinically significant episode of gastrointestinal bleeding within the previous 30 days. 15. Men and women of childbearing potential must be willing to consent to using effective contraception while on treatment and for at least 3 months thereafter. 16. At least 4 weeks since prior locoregional therapy including surgical resection, radiotherapy, hepatic arterial embolization or chemoembolization, radiofrequency ablation, percutaneous injection or cryoablation (treatment of target lesion only, non-target lesions can be treated with locoregional therapy). Provided the target lesion increased in size by 25% or more or the target lesion
--	---

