TOTAL EXPECTED NUMBER OF PATIENTS	Phase I component- 9-18 patients Phase II component-38 patients
PRE-, DURING AND POST-THERAPY TISSUE AND SERUM COLLECTION (Phase II component only)	Serum samples will be drawn for measurement of angiogenic markers, alfa-fetoprotein and inflammatory cytokines pre, during and post therapy. When feasible core biopsies will be obtained for tissue banking for research purposes and for routine H&E staining, pre and during therapy.
STUDY DRUG FORMULATIONS	Bavituximab: supplied as a sterile, preservative-free solution with 10 mM acetate at pH 5.0 and diluted with 0.9% (w/v) saline to a final volume of 100 ml. Sorafenib: information per package insert.

ROUTE OF ADMINISTRATION	Bavituximab: Intravenous (IV) Sorafenib: Oral
DOSE REGIMEN	Bavituximab: 0.3 mg/kg, 1.0 mg/kg or 3.0 mg/kg IV over 90 minutes weekly. Sorafenib: Initial dose 200 mg PO twice daily to be escalated to the target dose of 400 mg PO twice daily Phase I: Bavituximab and sorafenib are to be given for 1 cycle or 4 weeks. Phase II: Bavituximab and sorafenib are to be continued until disease progression or toxicity.
EVALUATION CRITERIA	Primary: Phase I: safety as measured by adverse events Phase II: efficacy as measured by time to progression using RECIST Version 1.1. Secondary: Phase II: 
 1. Safety and tolerability as assessed by NCI CTC v4.0 of this regimen in the phase II setting. 2. Overall survival, response rate and progression-free survival. 3. Correlation of serum and tissue markers of angiogenesis and immune response with treatment response.
DURATION OF STUDY PERIOD	Phase I: Patients will continue study treatment until 1 cycle of therapy. Phase II: Patients will continue study treatment until disease progression or toxicity.
ANTICIPATED STUDY DATES	Planned Start Date: February 2011 Planned Recruitment Closure: February 2013 Planned End Date: February 2014

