13.1.3 Target lesions

All measurable lesions up to a maximum of five lesions per organ and 10 lesions in total representative of all involved organs should be identified as **target lesions** and recorded and measured at baseline. Target lesions should be selected on the basis of their size (lesions with the longest diameter) and their suitability for accurate repeated measurements (either by imaging techniques or clinically). A

sum of the longest diameter (LD) for all target lesions will be calculated and reported as the baseline sum LD. The baseline sum LD will be used as reference by which to characterize the objective tumor response.

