13.2 Evaluation of target lesions

Complete Response (CR): Disappearance of all target lesions. The patient must be free of all symptoms of cancer.

Partial Response (PR): At least a 30% decrease in the sum of the longest diameter (LD) of target lesions taking as reference the baseline sum LD. Positive washing, brushing or biopsy and/or residual tumor may still be evident on endoscopy and/or CT scan. No lesion may increase in size and no new lesion may appear.

Progression (PD): At least a 20% increase in the sum of LD of target lesions taking as reference the smallest sum LD recorded since the treatment started or the appearance of one or more new lesions.

Stable Disease (SD): Neither sufficient shrinkage to qualify for PR nor sufficient increase to qualify for PD taking as references the smallest sum LD.

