15.1 Sample size calculation

The phase I component of the study will consist of a traditional 3+3 dose escalation rule with 3 or 6 patients in each cohort, the process for dose escalation is outlined in section 4.1.

The median TTP of patients with advanced HCC treated with sorafenib therapy is 5.5 months. Using this as a benchmark, we will enroll 38 patients, which will allow us to differentiate between a median TTP of 5.5 months and 8.3 months with 80% power and a two-sided significance level of 10% assuming a 24-month accrual and a 12-month follow-up period. TTP will be calculated from initiation of therapy to disease progression (intention to treat) as outlined in section 13.0. Removal from study as outlined in section 14 will be a censored event.

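### The synopsis measures primary-endpoint TTP by RECIST 1.1, but Section 15.1 takes progression from Section 13, which uses the 2000 criteria, and Section 14 adds a further progression definition tied to censoring

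*Combined protocol and SAP*

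**What the plan says.** The evaluation criteria in the synopsis (Section 1.0) give the Phase II primary measure as "efficacy as measured by time to progression using RECIST Version 1.1". The measurable-disease criterion in the synopsis is worded "according to Response Evaluation Criteria in Solid Tumors (RECIST, version 1.1) at least 2 cm with conventional techniques", and Section 6.1 names the same version.

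Section 15.1 states: "TTP will be calculated from initiation of therapy to disease progression (intention to treat) as outlined in section 13.0". Its next sentence makes removal from study under Section 14 a censored event.

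Section 13.1 says that response and progression will be evaluated "using the new international criteria proposed by the Response Evaluation Criteria in Solid Tumors (RECIST) Committee" and cites a journal article from 2000. Section 13.1.3 sets the target lesions as "All measurable lesions up to a maximum of five lesions per organ and 10 lesions in total". Section 13.2 calls progression when the sum of longest diameters rises by at least 20% from its smallest value, or when any new lesion appears. Version 1.1 is not mentioned anywhere in Section 13.

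Sections 8.1 and 8.2 refer to the RECIST criteria as defined by CTEP, without a version. The first removal criterion in Section 14 is a further definition of recurrence or progression: a new tumor larger than 1 cm, clinical progression in non-measurable sites, or an unequivocal change in size of the primary tumor.

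**The concern.** Phase II has one arm and judges its median TTP against an external figure of 5.5 months. No concurrent control group would absorb a difference in how progression is called, so the rule for the event has to be fixed in advance and be the same wherever the plan states it. Here the synopsis and the statistical section send the reader to differently identified criteria.

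The Section 14 wording adds a second problem. Progression is itself a reason for removal, its description there does not match Section 13, and removal is censored. Two analysts working from different sections could code the same patient as an event or as a censored observation. Such a choice is hard to make credibly once results are known.

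**Working it through.** **The rule for the primary event, place by place**

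| Place | Role | Criteria named or written |
|---|---|---|
| Synopsis, evaluation criteria | Names the primary endpoint | RECIST 1.1; no progression rule written out |
| Synopsis and 6.1, eligibility | Measurable disease at entry | RECIST 1.1; at least 2 cm conventional or 1 cm spiral CT |
| 8.1 and 8.2 | Baseline disease documentation | CTEP RECIST; no version |
| 13.1 to 13.4 | Response and progression | 2000 publication; 5 lesions per organ, 10 in total; 20% rise in the sum, or a new lesion |
| 14 | Removal for progression | New tumor over 1 cm, clinical progression, or unequivocal size change; no 20% rule |
| 15.1 | Calculates TTP | Progression by Section 13; Section 14 removal censored |

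Nothing in the documents says which source prevails. The reference in 15.1 leads to Section 13, and the synopsis leads to version 1.1.

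**Event or censored: Section 13 against Section 14**

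1. A new lesion of 1 cm or less is progression under 13.2, which sets no minimum size. It does not meet the new-tumor clause of Section 14.
2. Growth of metastatic target lesions can raise the sum by 20% while the primary tumor is unchanged and nothing new appears. That is progression under 13.2. The size clause in Section 14 refers only to the primary tumor.
3. A patient may be removed for clinical progression in non-measurable sites without meeting 13.2 or 13.3. Section 14 calls this progression. Under 15.1 it is a Section 14 removal and is censored.
4. A patient may meet both definitions. One sentence of 15.1 makes the progression the event, and the next censors the removal it causes.

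**Sample size, to see whether the point reaches it**

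Inputs from 15.1: medians of 5.5 and 8.3 months, 80% power, two-sided 10%, 24 months of accrual (A) and 12 months of follow-up (F). The plan names no formula. A one-sample log-rank test with exponential TTP and uniform accrual is assumed.

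- Hazard at a median of 8.3 months: λ1 = ln 2 / 8.3 = 0.0835 per month.
- Event probability: p1 = 1 − [exp(−λ1F) − exp(−λ1(A+F))] / (λ1A) = 0.8415.
- Expected null cumulative hazard per patient: e1 = 0.8415 × 8.3/5.5 = 1.270.
- n = [(1.645 × √1.270 + 0.842 × √0.8415) / (1.270 − 0.8415)]² = 37.6, that is 38.

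The stated 38 reproduces. Other formulas give other values: the log-hazard formula gives 36.5 events, and a Wald test on the hazard rate gives 47.0 patients. No term in the calculation depends on the RECIST version.

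**Secondary inconsistencies (response rate and consistency only)**

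- Section 13.1 says "Changes in only the largest diameter (unidimensional measurement) of the tumor lesions are used in the RECIST criteria", yet 13.2 adds for CR "The patient must be free of all symptoms of cancer".
- For PR, 13.2 adds "No lesion may increase in size and no new lesion may appear". The 13.4 table gives an overall PR for target-lesion PR with any non-target status short of progression.
- Eligibility accepts lesions of at least 2 cm or 1 cm. Section 13.1.1 requires more than 20 mm or 10 mm, and 13.1.2 calls less than those sizes non-measurable. A lesion of exactly 20 or 10 mm is left unclassified in Section 13.

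**The case against.** The strongest reply is that only one RECIST rule set is written out. The synopsis and eligibility text give a version label, with a size threshold in eligibility, but no version 1.1 rule for counting lesions or calling progression. Section 15.1 points expressly to Section 13, so a reader of the statistical section has one rule to apply. This stands in part. The conflict is between a named version and the criteria written out, not between two complete rule sets. It does not remove the contradiction, because the label sits in the definition of the primary endpoint and Section 13 never adopts it.

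Four stronger readings are tempting, and the documents do not support them.

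- **A known distortion of median TTP.** Scans are 6 weeks apart, so a call moved by one scan shifts that patient's TTP by 42/30.44 = 1.38 months. The documents do not say how many calls would move or in which direction, and they do not set out version 1.1. One patient's shift is not a shift in the median.
- **The added CR and PR conditions distort TTP.** Progression is a separate entry in 13.2, so they bear only on the secondary response rate. The PR clause stands under the target-lesion heading. Read as covering target lesions only, it agrees with the 13.4 table, so its scope is unclear rather than contradictory.
- **The measurability thresholds undermine the endpoint.** They matter only for a lesion of exactly 20 or 10 mm, and the sign in 13.1.1 may have lost its equality bar when the file was converted.
- **Section 15.1 censors every progression.** Its last sentence, taken alone, could be read that way. The sentence before it makes progression the endpoint, so this is ambiguity to remove and not a plan to analyze no events.

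**Conclusion.** The plan is wrong as written on this point. It contains an internal contradiction on the primary endpoint, which should be fixed. The synopsis names RECIST 1.1, Section 15.1 relies on a section built on the 2000 criteria, and Section 8 cites an unversioned source. Separately, Section 14 defines progression differently from Section 13 and feeds a censoring rule, so the choice of section may decide event status as well as event date.

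The effect on median TTP cannot be sized from the documents. They give neither the practical differences between versions nor the version behind the 5.5-month benchmark, so a mismatch with that benchmark is possible but not shown. The sample size of 38 stands, given the test assumed in the check. The contradiction itself rests only on the text and on the absence of any statement of which source prevails.

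**What to change.** 1. Name one RECIST version for TTP, PFS and response in the synopsis, Sections 6.1, 8.1, 8.2 and 13, and Section 15. Write Section 13 to that version. Version 1.1 is the natural choice because the primary endpoint names it, unless the sponsor confirms that the 5.5-month benchmark was measured by another.
2. State in Section 15.1 that progression by that version is the TTP event and is not censored through Section 14.
3. Reconcile the progression wording in Section 14 with Section 13, so that the documents carry one definition of progression. The sponsor decides the clinical content of the removal criteria.
4. For response rate and consistency, state the scope of the added CR and PR conditions in 13.2 or remove them, so that they agree with the 13.4 table and the diameter statement in 13.1. Align the measurability thresholds in the synopsis, 6.1, 13.1.1 and 13.1.2.

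The cost is protocol wording only, with no extra scans or patients.

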13.1.1 Measurable disease

Measurable lesions are defined as those that can be accurately measured in at least one dimension (longest diameter to be recorded) as > 20 mm with conventional techniques (PET, CT, MRI, x-ray) or as > 10 mm with a high-resolution CT scan. All tumor measurements must be recorded in millimeters or decimal fractions of centimeters. A “high-resolution” CT scan is one in which images are recorded at least every 5 mm.

13.1.2 Non-Measurable disease

All other lesions (or sites of disease), including small lesions (longest diameter < 20 mm with conventional techniques or < 10 mm using spiral CT scan), are considered non-measurable disease. Bone lesions, leptomeningeal disease, ascites, pleural / pericardial effusions, lymphangitis cutis/pulmonis, inflammatory breast disease, abdominal masses (not followed by CT or MRI), and cystic lesions are all non-measurable.

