6.0 CRITERIA FOR SUBJECT ELIGIBILITY

6.1 Subject Inclusion Criteria

1. Patients must have a diagnosis of hepatocellular carcinoma by at least one criterion listed below:
 - a. Histologically confirmed hepatocellular carcinoma
 - b. Axial imaging consistent with liver cirrhosis and at least one solid liver lesion ≥ 2 cm with early enhancement and delayed enhancement washout regardless of alpha-fetoprotein (AFP) levels.
 - c. AFP ≥ 400 ng/ml and evidence of at least one solid liver lesion ≥ 2 cm regardless of specific imaging characteristics.
2. Locally advanced or metastatic disease.
 - a. Patients with locally advanced disease must have disease deemed to be unresectable or not eligible for hepatic transplantation surgical oncologist or transplant physician.
 - b. Measurable disease, as defined as lesions that can accurately be measured in at least one dimension (longest diameter to be

measured) according to Response Evaluation Criteria in Solid Tumors (RECIST, version 1.1) at least 2 cm with conventional techniques or at least 1 cm with spiral computed tomography.

3. Child-Pugh Score A or B7.
4. Age \geq 18 years.
5. Eastern Cooperative Oncology Group (ECOG) Performance Score of 0-2.
6. Absolute neutrophil count \geq 1,200 cells/mm³.
7. Platelet count \geq 70,000 cells/mm³.
8. Total bilirubin \leq 3.0 mg/dl.
9. Hemoglobin \geq 8.5 g/dl.
10. INR \leq 1.8 (therapeutic anticoagulation allowed as long as medically indicated.)
11. Creatinine \leq 1.5 times upper limit of normal.
12. Women of childbearing potential must have a negative pregnancy test.
13. No clinically significant episode of gastrointestinal bleeding within the previous 30 days.
14. Men and women of childbearing potential must be willing to consent to using effective contraception while on treatment and for at least 3 months thereafter.
15. At least 4 weeks since prior locoregional therapy including surgical resection, radiotherapy, hepatic arterial embolization or chemoembolization, radiofrequency ablation, percutaneous injection or cryoablation (treatment of target lesion only, non-target lesions can be treated with locoregional therapy). Provided the target lesion increased in size by 25% or more or the target lesion was not treated with locoregional therapy.
16. Greater than 4 weeks since prior interferon therapy.
17. Greater than 4 weeks since prior and no concurrent use of rifampin or St John's wort.
18. Prior antiviral therapy is allowed.
19. Life expectancy $>$ 12 weeks.

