13.1.4 Non-target lesions

All other lesions (or sites of disease) that are not target lesions as defined in section 13.1.3 will be identified as **non-target lesions** and should also be recorded at baseline. Non-target lesions include measurable lesions that exceed the maximum numbers per organ or total of all involved organs as well as non-measurable lesions. Measurements of these lesions are required when feasible, since a patient may have progressive disease on the basis of larger non-target lesions. The presence or absence of each non-target lesion should be noted throughout follow-up.

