13.3 Evaluation of non-target lesions

Complete Response (CR): Disappearance of all non-target lesions and normalization of tumor marker level.

Non-Complete Response (non CR): Persistence of one or more non-target lesions or/ and maintenance of tumor marker level above the normal limits.

Progression (PD): Appearance of one or more new lesions. Unequivocal progression of existing non-target lesions. (Although a clear progression of "non-target" lesions only is exceptional, in such circumstances, the opinion of the treating physician should prevail, and the progression status should be confirmed at a later time by the reference radiologist (or study chair).

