Appendix B Child-Pugh Score

Measure	1 point	2 points	3 points
Total bilirubin (mg/dl)	<2.0	2.0-3.0	>3.0
Serum albumin (g/l)	>3.5	2.8-3.5	<3.5
INR	<1.7	1.7-2.2	>2.2
Ascites	None	Mild (based on clinical findings)	Severe (based on clinical findings)
Hepatic Encephalopathy	None	Controlled Medically	Refractory

5-6 points Child-Pugh A
 7-9 points Child-Pugh B
 10-15 points Child-Pugh C

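### Section 13 lets worsening ascites or effusions count as progression without asking whether the fluid is malignant, which can shorten the primary TTP

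*Combined protocol and SAP*

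**What the plan says.** The rule is built up over several sections of the protocol.

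- **13.1.2** classes as non-measurable a list that includes "Bone lesions, leptomeningeal disease, ascites, pleural / pericardial effusions". The list has no malignancy condition.
- **13.1.4** defines non-target lesions as the measurable lesions beyond the maximum number "as well as non-measurable lesions".
- **13.3** gives two routes to progression on non-target disease: "Appearance of one or more new lesions" and "Unequivocal progression of existing non-target lesions". For clear progression in non-target lesions alone, which it calls exceptional, it adds that "the opinion of the treating physician should prevail, and the progression status should be confirmed at a later time by the reference radiologist" or the study chair.
- **13.4** makes non-target progression overall progression whatever the target lesions show.
- **15.1** takes the primary TTP from Section 13, compares it with a fixed 5.5 months, and censors patients removed under Section 14.
- **6.1** admits "Child-Pugh Score A or B7", and no exclusion in 6.2 names ascites. **Appendix B** scores ascites as one of five liver-function items.

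**The concern.** The same finding has two meanings in this protocol. In Appendix B ascites is a sign of liver function. In Section 13 it is a site of disease whose worsening can end TTP. Section 2.0 describes the primary endpoint as radiographic time to progression, and Section 3.1 attributes the poor prognosis of advanced disease mainly to underlying liver dysfunction and limited treatment options. Fluid of hepatic origin is therefore to be expected here.

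Suppose a patient enters with mild ascites, the tumours stay stable, and the ascites becomes severe. Followed literally, Section 13 allows that to be recorded as progression, although no tumour has grown. Such records would shorten TTP and could mask a real effect of the combination. They would also put liver-disease events into the Cox regressions of TTP on tissue and serum markers (Section 15.2). In a single-arm trial no comparator carries the same error. The 5.5-month figure appears in Section 3.1 as the result of a trial in Child-Pugh A patients, whereas this trial also admits B7.

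**Working it through.** **1. Can a patient enter with ascites?** Appendix B has five items scored 1 to 3. With every other item at 1 point:
- mild ascites: 2 + 4 = 6, Child-Pugh A;
- severe ascites: 3 + 4 = 7, Child-Pugh B7.

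Both are eligible under 6.1.

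**2. Does any rule ask about the origin of the fluid?** No.
- The word unequivocal in 13.3 concerns how clear a change is, not its cause.
- The physician's opinion and later confirmation in 13.3 come with no criterion of malignancy.
- The aspirate or biopsy advice in 13.4 concerns complete response.
- The symptomatic-deterioration label in 13.4 applies only without objective evidence of progression, and fluid on a scan may be read as such evidence.

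**3. The plan's own figure.** Section 15.1 gives 38 patients for medians of 5.5 and 8.3 months, 80% power, two-sided 10%, 24 months of accrual and 12 of follow-up. It names no test. With exponential times and uniform accrual, the event probabilities are 0.931 (median 5.5) and 0.842 (median 8.3).
- Mean scale: N = [1.645 × 5.5/√0.931 + 0.842 × 8.3/√0.842]² / (8.3 − 5.5)² = 36.8, so 37.
- Log-hazard scale: (1.645 + 0.842)² / [ln(8.3/5.5)]² = 36.5 events; 36.5/0.931 = 39.2, so 40.

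The figure of 38 lies between these and is not in dispute.

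**4. Illustration of the effect.** The documents give no rate of new or worsening ascites, so a monthly hazard *h* of benign fluid scored as progression is assumed. The true tumour hazard is λ₁ = ln 2/8.3 = 0.0835.
- Recorded median = ln 2/(λ₁ + h).
- Share of recorded progressions that are not tumour progression = h/(λ₁ + h).
- Proportion with a fluid event first, by 6 months = [h/(λ₁ + h)] × [1 − exp(−6(λ₁ + h))].
- Power: simulated one-sample log-rank test, 38 patients, censoring uniform from 12 to 36 months, Z = (E − D)/√V > 1.645. D is the observed number of events and E is (ln 2/5.5) × total follow-up. V is either E or (D + E)/2.

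| h per month | Fluid event first by 6 months | Recorded median (months) | Non-tumour share | Power, V = E | Power, V = (D + E)/2 |
|---|---|---|---|---|---|
| 0 | 0% | 8.3 | 0% | 75% | 78% |
| 0.005 | 2.3% | 7.8 | 6% | 64% | 68% |
| 0.01 | 4.6% | 7.4 | 11% | 52% | 56% |
| 0.02 | 8.9% | 6.7 | 19% | 29% | 33% |
| 0.03 | 13.1% | 6.1 | 26% | 13% | 16% |

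**5. How far the table depends on its assumptions.** It takes every fluid event as scored, independently of tumour growth, and takes the benchmark as free of such events. Two variations at h = 0.03, with V = E:
- Only 25% of events scored: effective hazard 0.25 × 0.03 = 0.0075, power about 58%.
- Benchmark carries the same hazard: its tumour part is ln 2/5.5 − 0.03 = 0.096. Multiplied by 5.5/8.3 this is 0.0636, and adding 0.03 gives 0.0936. Power is about 52%.

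**6. Direction.** With a true median of 5.5 months, a hazard equal to 10% per 12 months (0.0088 per month) lowers the simulated upper-tail false-positive rate from about 3.9% to 1.3% (V = E). The error is conservative.

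**The case against.** The strongest reply is that 13.1.2 is a rule about measurability. It says these findings cannot be measured, not that all ascites is tumour, and its wording about lesions and sites of disease may presuppose tumour involvement. Section 13.3 does not score worsening fluid automatically. Stable tumours with worsening ascites is exactly the non-target-only case, for which it calls for the physician's judgement and later confirmation, so a hepatic cause can be rejected there. This stands as a real safeguard and lowers the likely number of misclassified events. It does not remove the problem, because neither reader is told that origin matters.

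Four stronger readings are tempting, and the documents do not support them:

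- **That new ascites is a new lesion, hence progression.** No section says so, and Section 14 describes new disease as a new tumour. The scoring is possible but less clear than for worsening of recorded fluid.
- **That TTP must shorten.** Section 14 lists clinical progression at non-measurable sites and intercurrent illness among its removal reasons, and 15.1 censors Section 14 removals. The same event could be censored instead of counted.
- **That the trial enrols only cirrhotic patients.** Cirrhosis on imaging is one of three diagnostic routes in 6.1, and 4.2.2 asks for histology in phase II. The share of B7 patients is not given.
- **That power will be 13–16%.** That is the far end of an assumed range with every event scored.

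**Conclusion.** The gap is real and touches the primary endpoint. Read literally, Section 13 makes ascites and effusions non-target disease whose unequivocal worsening is progression. No rule separates hepatic from malignant fluid, and the eligible population can carry hepatic fluid from baseline. Where such events are counted, TTP is shortened and a benefit may be missed; a false claim of benefit becomes less likely.

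The direction follows from the text, given that the event is counted under Section 13 rather than censored under 15.1. The size does not follow. The recorded medians of 7.8 to 6.1 months and the accompanying power losses rest on assumed hazards, exponential times, full scoring and an unaffected benchmark. They show that even a few per cent of such events would matter with 38 patients, and they are not a forecast. The point merits a change of wording before analysis; it does not affect the sample size.

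**What to change.** 1. In 13.1.2 and 13.3 state that, for endpoint scoring, ascites and pleural or pericardial effusions count as non-target disease, and their appearance or increase as progression, only when judged malignant on the available evidence. That means any cytology already done for care, or imaging confirmed through the existing 13.3 review. Otherwise the fluid is recorded as an adverse event and does not count as progression.
2. Add one data field marking progression calls that rest on fluid alone, and report their number.
3. Add a sensitivity analysis of TTP in which all new or worsening fluid counts as progression. This is needed because the new rule may delay the progression date when malignant fluid is unproven, which would lengthen TTP.
4. Reconcile the progression wording in Section 14 with the censoring sentence in 15.1, so that one event cannot be progression in one place and censored in another. This concerns scoring only; which patients leave treatment is for the sponsor and investigators.

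The cost is wording in two subsections, one data field, one extra analysis and the reconciliation. No visit, procedure or patient is added. The main downside is the possible delay described in item 3, which the sensitivity analysis makes visible.
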